# 9.2.2. Disposition Information

The following tabulations will be provided by treatment group and overall:

- The number of subjects screened, randomized and not-randomized, with the reason for not being randomized. Number randomized and not treated.
- Number of subjects randomized per country and investigator.
- The number (percent) of subjects in the different analysis populations as defined in Section 3.
- Descriptive statistics of the duration of the analysis periods will be provided.
- The number (percent) of subjects per analysis window as defined in Section 6.3 for analysis.
- Number of subjects with a deviation of more than the number of days allowed per protocol from the target of the analysis windows, per window.
- In addition, descriptive statistics will be provided of the number of days distance from the target of the window, as specified in the protocol, as well as of the relative day per window. These will allow to assess if the later visits (especially the close-out visits) are done close to scheduled visits.
- Overall summary of number of subjects (percent) per number of missed and virtual visits due to COVID-19 per treatment group
- Summary of number of subjects (percent) with missed, virtual visits due to COVID-19, missed visits not due to COVID-19 and complete visits per study visit and treatment group
- The number (percent) of subjects with completion/discontinuations and the reasons for discontinuation from study and from IP. This table will also be provided by stratum.
- The number (percent) of subjects with discontinuations due to COVID-19 and the reasons for discontinuation from study and from IP.
- Kaplan-Meier estimates (graphical and tabular) of the time in the study, defined as time from the date of the first intake of IP to the last contact in the study, excluding data from the vital status eCRF. See Section 6.5 for the censoring rules.
- Kaplan-Meier estimates (graphical and tabular) of the time on treatment, defined as time from the date of the first to last intake of IP.

If a high number of discontinuations is seen in a blinded fashion during the course of the study, more descriptions may be added to further investigate the reasons for discontinuations over time. Details will then be added to this SAP before unblinding for the final analysis.

In addition, the following listings will also be provided:

- Subjects receiving investigational product from specific batches, where more than one batch
  was used (showing the batch numbers of the investigational products actually used, including
  the expiration dates),
- Randomization scheme and codes (subject identification, treatment assigned, with a flag if the code was broken and the reason).
- Date of the earliest ICF signed for this study and date of last scheduled visit performed in this study.
- Listing of missed and virtual visits due to COVID-19.
- Listing of Study and/or study drug discontinuations due to COVID-19
- Listing of comments containing information related to COVID-19

# 9.2.3. Protocol Deviations and Eligibility

Listings will be provided for the subjects excluded from the different analyses sets with the reason for exclusion.

Tabulation per treatment group (and overall) of the major protocol deviations *impacting the efficacy analyses* will be provided. The same table will also be provided by stratum. A listing will be provided for all major protocol deviations *with a flag indicating which impact efficacy analyses and are thus excluded from the PP analysis.* 

Tabulation per treatment group (and overall) of the number (percent) of subjects with major protocol deviations related to COVID-19, overall and per COVID-19 related protocol deviation will be provided. Listings of major and minor COVID-19 related protocol deviations will be created.

# 9.2.4. Medical History and Concomitant Diseases

Frequency tabulations per treatment group (and overall) per system organ classes and preferred terms will be provided for the medical history findings (i.e. condition no longer present at the start of the study) as well as for the concurrent diseases (i.e. conditions present at the start of the study).

# 9.2.5. Prior and Concomitant Therapies

# 9.2.5.1. Classification of Therapies

All prior and concomitant therapy records will be categorized as follows, considering their date and flags indicating the relative timing versus study (drug) start or end (before, after, ongoing...):

- Prior only: when the record ended before the first IP administration date.
- Concomitant only: when the record started on the same date or after the first IP administration date.

- Prior and concomitant: when the record started before the date of first IP administration, and ended on a date after first IP administration (or on the same date), or continued.

Records without a start date are assumed to have started before the date of first IP administration. Records without an end date are assumed to be ongoing.

When the start or end date of the prior and concomitant therapy records are incomplete, the date of first IP administration will be considered to the same level of information provided by these incomplete dates in order to categorize the timing of these records. This means a record only having month and year will be categorized comparing only to the month and the year of the date of first IP administration. If the start date is unknown but the medication is flagged to have started prior to the first dose of IP, this information will be taken into account.

For both the start and the end dates of the concomitant therapy records, their day relative to the day of first IP administration will be calculated as described in Section 6.1.

# 9.2.5.2. Coding of Therapies

All therapies are coded using WHO Drug coding. In the table(s), the generic term will be used. The anatomical therapeutic classification (ATC) classes level 2 and 4 will be used for analysis. Multiple records of the same generic term for the same subject with the same categorization will be counted only once. The table will therefore present subjects, not occurrences.

# 9.2.5.3. Analyses

A frequency tabulation per treatment group (and overall) of the ATC classes level 2 and 4 and generic terms of the prior medications (defined as 'prior only' or 'prior and concomitant') will be provided and as well as of the concomitant medications (defined as 'concomitant only' or 'prior and concomitant').

Additional tables will be created for respiratory-related concomitant and prior medications. The definition of respiratory-related medications will be provided in a separate document before unblinding for the final study report.

Similar tables will be provided restricted to medications taken up to 30 days after the last dose of *IP*.

# 9.2.6. Exposure to IP and Compliance

The following parameters will be calculated for the compliance and extent of exposure to IP:

- Overall compliance (%) = 100 x (number of tablets actually used) / (number of tablets that should have been used, according to the randomization).
- Total treatment duration (days) = last dose of IP intake date first dose of IP intake date + 1 day.
- Total treatment duration, excluding days off drug (days): sum of all durations (last first +1) in the drug log pages where there is at least one dose taken, i.e. the sum of the number of days with at least one dose of IP.

- Percentage days with an intake =  $100\% \text{ x} \left(\frac{\text{total treatment duration, excluding days off drug}}{\text{total treatment duration}}\right)$
- Total compliant treatment duration (days): sum of all durations (last first +1) in the drug log pages where there is a dose with exactly 3 tablets.
- Percentage compliance of treatment duration =  $100\% \times \left(\frac{\text{total compliant treatment duration}}{\text{total treatment duration}}\right)$

Similar calculations will be done using only the data up to Week 52.

Summary tables will be provided for the different compliance and extent of exposure parameters by treatment and overall. In addition, frequency tables will also be provided for the compliance parameters (overall compliance, percentages days with an intake and percentage compliance of treatment duration), using the following categories: <80%,  $\ge80\%$ -<100%, 100%, >100%- $\le120\%$ , >120%.

Frequency tables with the number of subjects who had at least one down-titration and with the number of subjects who had at least one dose interruption, and the reasons for down-titration and interruption by treatment group and overall, will also be provided.

Patient-years of exposure to IP by treatment group and overall.

The same tables will be created by stratum and treatment.

A listing will be provided of the subjects who took incorrect IP for at least part of the treatment period, all prime therapy records are to be included to provide an overview of the amount of incorrect treatment relative to the total treatment period.

In addition, listings of the subjects who had their IP down-titrated and interrupted for at least part of the treatment period will be provided, all prime therapy records are to be included to provide an overview of the amount of down-titration and interruption relative to the total treatment period.

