Each subject will have a screening period of maximum 28 days. The duration of study treatment for individual subjects will vary from 52 weeks for the last enrolled subject to e.g. 132 weeks for the first enrolled subject (assuming a recruitment period of 80 weeks, the actual duration will depend on the actual time to recruit subjects for the study). A follow-up visit (at the clinical study center or by phone call, decided by the investigator) is planned 4 weeks after the EoST/end of study assessment (EoSA) visit.

At the end of this study, treatment with IMP in an optional extension study (under a separate study protocol) may be offered to all eligible subjects, provided Independent Ethics Committee (IEC)/Institutional Review Board (IRB) and Competent Authority approvals for such an extension are granted.

To protect the safety and integrity of the study data, an independent data monitoring committee (IDMC) will be implemented, as well as a clinical endpoint adjudication committee (CEAC). Charters are in place for all committees. For additional information, refer to Sections 8.1 (for IDMC) and 8.2 (for CEAC).

For detailed information regarding dosage form, packaging, and labeling of the IMP, please refer to Sections 5.2 and 5.3.

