4.1.2. Guidance for dose modification in case of adverse events

At any stage, the investigator can decide to permanently discontinue IMP for concerns regarding safety and tolerability, i.e. an AE including clinically significant abnormal laboratory tests. For abnormal liver function tests (LFTs), specific guidance is described in Appendix 9.

For the subsequent management of these AEs, the investigator can reduce the dose, interrupt, or permanently discontinue the IMP. Down-titration will be a one-step process to the lowest reduced dose. Once the AE has stabilized or improved, the dose can be increased again (re-escalation). For the re-escalation from the lowest reduced dose, an intermediate reduced dose level is required (Figure 2).

[figure not shown]

Figure 2: Study Drug Dose Modification: Down-titration and Re-escalation Steps

Tablet colors are for illustration purposes only

For all AEs, the investigator is advised to evaluate the concomitant medication, including local standard of care for the treatment of IPF, as part of the benefit-risk evaluation. The recommended duration of a different dose level or interruption for elevated LFTs is at least 2 weeks.

Elevated LFTs

At Visit 3 (randomization visit), blood samples are collected before IMP intake and the results of the laboratory tests will only be known after IMP intake. Therefore, if the LFTs are abnormal at this visit, the investigator needs to discontinue IMP (only if aspartate aminotransferase [AST] or alanine aminotransferase [ALT] $\geq 1.5x$ upper limit of normal [ULN], total bilirubin $\geq 1.5xULN$, and/or gamma glutamyl transferase [GGT] $\geq 3xULN$). It is recommended to consult the contract research organization (CRO) medical monitor (as per study contact list) or sponsor's study physician (if the former is not available).

At any visit from Visit 4 onwards:

Continue as planned: AST or ALT $\geq 1.5x$ to $3xULN$.

Discontinuation of IMP:

- AST or ALT >8xULN: permanently discontinue IMP with close observation*.
- AST or ALT \geq 3xULN with signs or symptoms of severe liver damage**: permanently discontinue IMP with close observation*.
- AST or ALT \geq 3xULN for more than 2 weeks
- AST or ALT \geq 3xULN during re-escalation (described below)

Down-titration to reduced dose level or interruption of IMP:

- AST or ALT \geq 3x to 5xULN without signs of severe liver damage**:

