Down-titrate to low (reduced) dose level or interrupt IMP for at least 2 weeks (to be decided by the investigator, based on the subject's risk assessment).
- AST or ALT \geq 5x to 8xULN without signs of severe liver damage**:
Interrupt IMP for at least 2 weeks.

During these periods of at least 2 weeks: Re-test AST, ALT, alkaline phosphatase, total bilirubin, and eosinophils within 48 to 72 hours, approximately at 7 days, thereafter approximately at 14 days, and also assess signs of severe liver damage**. If local regulations allow, home visits can be performed if subjects cannot come to the clinical study center.

Re-escalation after each period of at least 2 weeks at any dose level:

- Remain on the highest tolerated dose at investigator's discretion. Monitoring of LFTs can return to the planned study assessments once the LFTs have stabilized at the highest tolerated dose level for 8 weeks.
- AST and ALT <3xULN:
Re-escalate to the next dose level for at least 2 weeks, with regular LFT monitoring (weekly for the first 2 weeks, biweekly for the following weeks, or more frequently at investigator's discretion) and repeat re-escalation to next higher dose level every 2 weeks (or longer at investigator's discretion) if AST and ALT <3xULN.
- AST or ALT \geq 3xULN:
Discontinue IMP.

*Close observation is defined as:

- Monitor two to three times per week all of the following parameters: ALT, AST, alkaline phosphatase, total bilirubin, eosinophils, and International Normalized Ratio (INR). If local regulations allow, home visits can be performed if subjects cannot come to the clinical study center.
- Frequency of retesting can be reduced to once a week or less if abnormalities stabilize or the IMP has been discontinued; however, monitoring might still be needed more frequently taking into consideration the standard of care and/or changes to this.
- Re-query history of symptoms, prior and concurrent diseases, concomitant medication and non-prescription medicines, herbal, dietary supplements, alcohol use, recreational drug use, special diets.
- Rule out all of the following: acute viral hepatitis, auto-immune hepatitis, alcoholic hepatitis, non-alcoholic fatty hepatitis, hypoxic/ischemic hepatitis, biliary tract disease, and cholestasis.
- Re-query exposure to environmental chemical agents.

– Consider gastro-enterology or hepatology consultations.

** Signs of severe liver damage:

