- Increase of liver transaminases is accompanied by appearance of fatigue, nausea, vomiting, right upper abdominal quadrant pain or tenderness, fever, rash and/or eosinophilia (>5%), and/or
- Total bilirubin ≥ 1.5 x ULN, or
- INR >1.5.

Each blinded treatment kit will have blisters for the high (original) dose level, intermediate (reduced) dose level, and low (reduced) dose level, allowing the clinical study center to modulate the IMP dose for a particular subject, even without knowing the original treatment allocation (also see Section 5.2).

The Investigator will be responsible for managing COVID-19 infected subjects and the decision to continue or interrupt IMP for subjects with confirmed or suspected cases of COVID-19 infection is at the investigator's discretion. Guidance on continuation of IMP and requirements for assessments conducted during the COVID-19 pandemic are provided in Section 6.1.1.

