5.2. Dosage and Administration

The following doses will be tested; three tablets will be provided per dose (high [original] dose level):

- GLPG1690 600 mg q.d. (as three GLPG1690 200-mg tablets)
- GLPG1690 200 mg q.d. (as one GLPG1690 200-mg tablet and two placebo tablets, matching the GLPG1690 200-mg tablet)
- placebo q.d. (as three placebo tablets, matching the GLPG1690 200-mg tablet)

The following doses will be provided for down-titration and re-escalation; two tablets will be provided per dose:

Low (reduced) dose level:

- GLPG1690 200 mg q.d. (as one GLPG1690 200-mg tablet and one placebo tablet, matching the GLPG1690 100-mg tablet)
- GLPG1690 100 mg q.d. (as one GLPG1690 100-mg tablet and one placebo tablet, matching the GLPG1690 200-mg tablet)
- placebo q.d. (as one placebo tablet, matching the GLPG1690 200-mg tablet and one placebo tablet, matching the GLPG1690 100-mg tablet)

Intermediate (reduced) dose level:

- GLPG1690 400 mg q.d. (as two GLPG1690 200-mg tablets)

- GLPG1690 200 mg q.d. (as one GLPG1690 200-mg tablet and one placebo tablet, matching the GLPG1690 200-mg tablet)
- placebo q.d. (as two placebo tablets, matching the GLPG1690 200-mg tablet)

Refer to [Figure 2](#) in Section 4.1.2 for an overview of number of tablets to be taken per dose level.

The IMP is to be taken q.d. at the same time every day with food (e.g. breakfast, small meal, or a snack) or after food intake, taking into account the timing of the planned visits, with a maximum of 2 hours between the food intake and IMP intake. Subjects will be instructed to swallow the tablets as a whole with a glass of water and to not chew the drug prior to swallowing. On visit days, subjects will be instructed to take their IMP at the clinical study center, to allow for predose (i.e. before IMP intake) assessments to be completed.

At Visits 3, 9, and 12, the subject will be asked to take pirfenidone or nintedanib (if applicable) at the clinical study center.

If a subject misses a dose (e.g. because he/she forgot to take the medication), he/she should take the missed dose within 12 hours after the planned intake time and within 2 hours of food intake. If the IMP is not taken within 12 hours after the planned time, the missed dose should be skipped.

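### SAP 9.2.6 counts a day as compliant only if three tablets were taken, so a subject who follows a prescribed two-tablet reduction scores below 100% (minor)

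*SAP*

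**What the plan says.** SAP 9.2.6 defines total compliant treatment duration by summing the days "in the drug log pages where there is a dose with exactly 3 tablets". It divides this by total treatment duration, which runs from first to last dose whatever level was prescribed in between. A second parameter, overall compliance, divides tablets used by the "number of tablets that should have been used, according to the randomization". A third, percentage days with an intake, counts any day with at least one dose. All three are tabulated in categories that include below 80% and exactly 100%.

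The same section plans frequency tables of subjects with a down-titration or an interruption, with reasons. It also plans listings of those subjects "to provide an overview of the amount of down-titration and interruption relative to the total treatment period".

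Protocol 5.2 gives three tablets a day at the original level in each arm. For the low and intermediate levels it states: "The following doses will be provided for down-titration and re-escalation; two tablets will be provided per dose". This holds in all three arms, placebo included. Protocol 4.1.2 lets the investigator reduce the dose for adverse events. For one band of raised liver tests it says "Down-titrate to low (reduced) dose level or interrupt IMP for at least 2 weeks", and on the way back up "For the re-escalation from the lowest reduced dose, an intermediate reduced dose level is required". It also lets a subject stay on the highest tolerated dose.

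SAP 9.1 drops only the version of the exposure and compliance analyses restricted to data up to Week 52. The whole-study tables remain.

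**The concern.** A day at a prescribed reduced level is always in the denominator of the duration measure and can never be in its numerator, because the prescribed count is two and the rule demands three. A subject who does exactly as instructed is therefore scored as partly non-compliant.

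The rule also orders subjects wrongly. By Protocol 4.1.2, "Each blinded treatment kit will have blisters for the high (original) dose level" and for both reduced levels, so a subject told to reduce has the three-tablet blisters to hand. One who carries on with three tablets scores 100%, above one who followed the instruction.

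What is at stake is how the compliance tables in the abbreviated study report are read. The counts at 100% and below 80% would mix missed tablets with reductions ordered by the investigator.

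**Working it through.** The plan states no compliance figure, so there is none to reproduce. The check applies the SAP 9.2.6 definitions directly.

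**Inputs**
- Tablets a day: 3 at the original level, 2 at either reduced level (Protocol 5.2).
- Shortest liver-test cycle without interruption: 2 weeks low plus 2 weeks intermediate = 28 days (Protocol 4.1.2).
- Treatment duration D: 365 days (the Week 52 visit day) and, as the protocol's own example of a long stay, "132 weeks for the first enrolled subject", which is 132 × 7 = 924 days.

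**Duration measure.** For a fully adherent subject with r reduced days and no interruption:

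100 × (D − r)/D = 100(1 − f), where f = r/D.

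- r = 28, D = 365: 337/365 = 92.3%.
- r = 28, D = 924: 896/924 = 97.0%.
- r = 1, D = 365: 364/365 = 99.7%, so one reduced day removes the subject from the 100% category.
- Below 80% requires r > 0.20D. For D = 365 that is r > 73.0, so 74 days or more (291/365 = 79.7%). For D = 924 it is r > 184.8, so 185 days or more (739/924 = 79.98%).

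**Overall compliance, only if the denominator is three tablets a day throughout:**

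100 × (3(D − r) + 2r)/(3D) = 100(1 − f/3).

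- r = 28, D = 365: (337 × 3 + 28 × 2)/1095 = 1067/1095 = 97.4%.
- r = 28, D = 924: 2744/2772 = 99.0%.
- Below 80% requires r > 0.60D: 220 or more of 365 days, 555 or more of 924.

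**Four subjects over 365 days, present rules** (overall figures conditional as above)

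| Behaviour on 28 days | Duration | Overall | Days with an intake |
|---|---|---|---|
| Prescribed two, took two | 92.3% | 97.4% | 100% |
| Prescribed three, took two | 92.3% | 97.4% | 100% |
| Prescribed two, took three | 100% | 100% | 100% |
| Took none, uninstructed | 92.3% | 92.3% | 92.3% |

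The first two rows cannot be told apart on any of the three measures, and the third outranks the first.

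**Duration measure with a compliant day defined by the prescribed level**, same denominator: row 1 becomes 365/365 = 100%. Rows 2, 3 and 4 each become 337/365 = 92.3%.

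**The case against.** The best defence is that the tables are descriptive and decide nothing. SAP 3.4 and 9.1 drop the per-protocol analysis, and SAP 9.1 also drops the on-treatment sensitivity analysis. The programme has ended with no marketing application. The below-80% band is only a table category; nothing in the documents ties it to an exclusion. The minimum 28-day cycle does not reach that band. All of this stands, and it sets the severity.

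The second argument is that the same section already supplies context: days with an intake, the down-titration and interruption tables with reasons, and the listings. There is also a listing of subjects who took incorrect IP, which might catch the subject who ignored a reduction, although the term is not defined. This stands in part. A reader can reconstruct the position subject by subject, but none of these outputs corrects the percentage or its category counts.

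The third argument is that overall compliance names the randomized regimen as its reference, so on the three-a-day reading it openly states its own yardstick. That is fair. A reader might infer that overall compliance is wrong in the same way. Three a day is the natural reading, but the SAP does not say how the expected tablets are counted, and it places technical derivations in a separate document. The inference stays conditional.

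A reader might also infer that the treatment arms would be distorted unequally. The documents give no down-titration rates, so this cannot be claimed.

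Finally, a reader might want instructed interruptions to count as full compliance. That is a different question, and the answer depends on whether such days join the numerator or leave the denominator. With D = 365, 100 instructed interruption days and 28 missed days, the first gives 337/365 = 92.3% and the second 237/265 = 89.4%. The second also departs from the first-to-last-dose duration in Protocol 7.3.5.1, which disregards temporary interruptions.

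**Conclusion.** The defect in the duration measure is explicit and needs no interpretation: the SAP requires three tablets on days when the protocol prescribes two. Under-scoring of a fully adherent subject equals the share of days at a reduced level: 7.7 percentage points for 28 of 365 days, 3.0 for 28 of 924. It affects tables that will still be produced. These figures assume full adherence and no interruption.

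For overall compliance the effect is one third as large, and it exists only if the denominator is three tablets a day throughout.

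Severity is minor. No efficacy analysis is affected and no difference between arms is claimed.

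**What to change.** In SAP 9.2.6, count a day as compliant when the tablets taken equal the number for the dose level prescribed that day: three at the original level, two at either reduced level, as Protocol 5.2 already sets out. Keep total treatment duration as the denominator. Leave interruption days as now handled, in the denominator and not in the numerator. Leave percentage days with an intake unchanged.

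For overall compliance, state how the expected tablets are counted. If the count is three a day throughout, apply the same level-specific counts.

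The cost is a short wording change and some programming. The redefinition needs the prescribed level for each day. Protocol 5.5 has changes and interruptions recorded on the diary card, and SAP 9.2.6 already plans listings of down-titrated subjects with their therapy records, but neither shows that the prescribed daily level is a database variable. If it is not, retitle the measure *percentage of days at the full randomized tablet count*, which costs only table titles.

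Part of the study team is already unblinded (SAP 2.7), so either change should be documented with its reason in the study report, as SAP 9.1 provides.
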